#### **14.3.2. Parameters of the Glucose Metabolism**

By patient lists will be provided with all measurements (HbA1c, insulin, glucagon, concurrent glucose) along with the unit, normal range, any deviation from it, and the relevance of being outside the normal range, identified by the investigator. Visit labels will be provided describing the timing of the sampling to the dosing and to the meals.

Descriptive statistics will be presented (mean, SD, median, minimum, and maximum) by time points.

The change from the baseline value, measured pre-dose on Day-1 will be calculated and summarized in tabular and graphical formats for HbA1c.

The time- and food status-matched change from baseline at insulin, glucagon and concurrent glucose will be calculated in the following way: every time point on Day 1 and Day 14 will have the own baseline value from Day -1, considering fasting conditions or their timing to meals.

Additional list will be created of patients with clinically significant abnormal values along with the abnormal parameter.

#### **14.3.3. Antibodies to BIM23B065**

A by-patient listing will be created containing the results of antibody assessments by visits.

A frequency table will be created to present the number and percentage of subjects developing antibodies, by visits.

#### **14.3.4. Endocrine Parameters**

By patient lists will be provided with all measurements along with the unit, normal range, any deviation from it, and the relevance of being outside the normal range, identified by the investigator.

Descriptive summaries will be presented from the measured values and from the calculated change from baseline (Day -1).

**Protocol code:** D-FR-10380-002

**Protocol Title:** A phase IIA, open-label, single-arm, two stage, multi-centre study to investigate the pharmacodynamics, pharmacokinetics, safety and tolerability of repeated subcutaneous administration of BIM23B065 in subjects with acromegaly

Additional list will be created of patients with clinically significant abnormal values along with the abnormal parameter.

#### **14.4. Gallbladder Echocardiography**

By patient list will be provided with all assessments and all time points. The presence of lithiasis and sludge, the result and the description of abnormality will be presented. The number and percentage of patient with lithiasis and sludge will be.

#### **14.5. Physical Examination**

Physical examination data will be presented in a by-patient listing along the reason if it was not done at each time point.

#### **14.6. Pregnancies**

Pregnancy data will be shown in a data listing. No special analysis will be performed on the pregnancy data. Subjects are to be discontinued from the study if they become pregnant.

### **15. OTHER PLANNED ANALYSIS**

#### **15.1. Pharmacometrics**

Details regarding PK, and PK/PD modelling will be described in a separate Pharmacometric Analysis Plan.

#### **15.2. Tumour tissue receptor expression and drug response**

Subjects with available tumour tissue specimen will be categorized according to the SSTR2, SSTR5 and D2 receptor expression status. Incidence tables for tumour tissue categories will be presented.

The number and proportion of GH responders, subjects with an IGF-1<ULN (age normalized) on Day 14, and subjects with a PRL<ULN (gender normalized) on Day 14 will be presented by the receptor expression status.

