### 5.1.3. Exploratory Objectives

- To correlate GH, Insulin-like Growth Factor-1 (IGF-1) and Prolactin (PRL) responses with expression of Somatostatin Receptor 2 (SSTR2), Somatostatin Receptor 5 (SSTR5) and Dopamine receptor sub-type 2 (D2) in pituitary tumour tissues, when available.
- To assess anti-drug antibodies (ADA).

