### **5.2.3. Exploratory Endpoints and Evaluations**

- Assessment of ADA.
- Exploration of the relationship between response to BIM23B065 and the expression of SSTR2, SSTR5 and D2 in those subjects with available tumour tissue.

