### 10.7. Derived and Computed Variables

The following derived and computed variables have been initially identified. It is expected that additional variables could be required. The SAP will not be amended for additional variables unless they are directly related to the primary endpoint or key secondary efficacy variables. Any additional derived or computed variables will be identified and documented in the ADaM requirement documentation and/or in the footnotes of the outputs, where appropriate.

Variable Name	Description	Valid values (Ranges)	Computation methods, Notes or equation(s)
OTPDMEN	Mean GH over 6 hours after octreotide dosing during Octreotide Test	0-200 ug/L	= [SUM(GH measurements 1, 2, 3, 4, 5, 6 hours post octreotide dose)]/number of valid GH measurements
OTRBL	Reduction from Baseline in GH level during Octreotide Test	0-100 %	= [1- (OTPDMEN/ Baseline GH level)] x 100
GHMDX	Mean GH over 6 hours measured on DayX	0-200ug/L	= [SUM(GH measurements 1, 2, 3, 4, 5, 6)]/number of valid GH measurements over 6 hours on DayX]

Protocol code: D-FR-10380-002

Protocol Title: A phase IIA, open-label, single-arm, two stage, multi-centre study to investigate the pharmacodynamics, pharmacokinetics, safety and tolerability of repeated subcutaneous administration of BIM23B065 in subjects with acromegaly

Variable Name	Description	Valid values (Ranges)	Computation methods, Notes or equation(s)
GHRGL	Reduction from Baseline in GH level on DayX	0-100 %	= [1- (GHMDX/GHM(D-1))] x 100

As a general rule mean will be calculated by summarizing the available valid (non-missing) measurements and divided by the number of measurements. Percent change from baseline will be calculated according to the following:  $[1 - (\text{present value}/\text{baseline value})] \times 100$ .

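### The exploratory objective is to correlate hormone responses with receptor expression, but SAP 15.2 only counts binary responders by expression status and gives no measure of association

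*SAP*

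**What the plan says.** SAP 5.1.3 states the objective: "To correlate GH, Insulin-like Growth Factor-1 (IGF-1) and Prolactin (PRL) responses with expression of Somatostatin Receptor 2", and likewise SSTR5 and D2, "in pituitary tumour tissues, when available". The matching endpoint in 5.2.3 is worded more loosely: "Exploration of the relationship between response to BIM23B065 and the expression of SSTR2, SSTR5 and D2 in those subjects with available tumour tissue".

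The analysis is in 15.2: "Subjects with available tumour tissue specimen will be categorized according to the SSTR2, SSTR5 and D2 receptor expression status". After incidence tables of the categories comes "The number and proportion of GH responders, subjects with an IGF-1<ULN (age normalized) on Day 14", together with subjects whose Day 14 PRL is below the gender-normalised limit. These counts "will be presented by the receptor expression status". The section does not give the number of categories, the assay scale or the cut-points, and it names no measure of association.

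Continuous outcomes are available. Section 10.7 derives GHRGL, the "Reduction from Baseline in GH level on DayX", and gives a general formula for percent change. Section 13.2.1 summarises percent change in GH, and 13.2.2 does so for IGF-1 and PRL. None of these is set against receptor expression. The separate Pharmacometric Analysis Plan covers PK and PK/PD modelling (3.2, 15.1), so nothing in the SAP assigns this analysis to it.

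**The concern.** An objective that asks for a correlation is served by an analysis that cannot produce one. Both sides of the relation are reduced to classes: expression to a status, and each hormone outcome to yes or no. Two subjects with 55% and 95% GH reduction then count the same, as do two subjects at opposite ends of one expression category.

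The loss matters because the numbers are small. Section 8 caps evaluable subjects at 24, 12 per stage. If at least 8 of 12 respond on BID, 7.2 says the TID part is not run, so the ceiling is then 12. Tissue is available only for some subjects. At the 75% responder rate assumed in section 8, 12 subjects include about 12 × 0.25 = 3 non-responders, who are then spread over the expression categories of each receptor. A count table of that size says little about whether higher expression goes with deeper suppression.

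**Working it through.** **1. The SAP's own figure.** The SAP gives no precision or power for the receptor analysis. Its only power figure, in section 8, is for the primary test: over 84% with n = 12, null rate 33% and alternative 75%, one-sided 5%. It reproduces: P(X ≥ 8 | 12, 0.75) = 0.842, with type I error P(X ≥ 8 | 12, 0.33) = 0.018; a cut at 7 would give 0.063. It enters here only through the sample size and the two responder rates.

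**2. Information kept by cutting a variable.**

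- Inputs from section 8: responder rates of 33% to 75%, maximum n of 24.
- Assumed: share of receptor-positive subjects 25% to 75%; number of categories two or three; normally distributed underlying variables.
- Formula: splitting a normal variable with a share p on one side keeps E(p) = φ(z_p)² / [p(1 − p)] of the information on a correlation, where z_p is the normal quantile and φ the normal density. With both variables split, the two factors multiply.

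Single factors:

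- E(0.50) = 0.3989² / 0.25 = 0.637
- E(0.33) = 0.3621² / 0.2211 = 0.593
- E(0.25) = E(0.75) = 0.3178² / 0.1875 = 0.539

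| Responder rate | Receptor-positive 25% or 75% | Receptor-positive 50% |
|---|---|---|
| 33% | 0.593 × 0.539 = 0.32 | 0.593 × 0.637 = 0.38 |
| 50% | 0.637 × 0.539 = 0.34 | 0.637 × 0.637 = 0.41 |
| 75% | 0.539 × 0.539 = 0.29 | 0.539 × 0.637 = 0.34 |

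So 29% to 41% is kept with a binary status.

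With three equal ordered categories and optimal scores, the expression factor is (2/3) × (3 × φ(0.431))² = (2/3) × (3 × 0.3636)² = 0.793. The products are 0.793 × 0.539 = 0.43, 0.793 × 0.593 = 0.47 and 0.793 × 0.637 = 0.50. So about 43% to 50% is kept.

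**3. What a correlation would deliver.** Approximate 90% interval for Spearman: tanh[atanh(r) ± 1.645 × √(1.06/(n − 3))]. For an observed r of 0.5, atanh(r) = 0.549.

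- n = 12: 0.549 ± 1.645 × 0.343 = −0.015 to 1.114, which gives −0.02 to 0.81.
- n = 24: 0.549 ± 1.645 × 0.225 = 0.180 to 0.919, which gives 0.18 to 0.73.

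**4. Why a power comparison is not used as the measure of size.** One can simulate Spearman's test against Fisher's exact test on a median split, both at nominal two-sided 10%. With n = 12 and a true correlation of 0.7, Spearman detects it in 78% of data sets and Fisher in 32% (50% responders) or 15% (75% responders). At a correlation of 0.5 the figures are 47% against 16% or 8%. With no correlation at all, however, Spearman rejects in about 10%, but Fisher in only about 4% or 2% at n = 12 and below 1% at n = 8. With 8 subjects split 4 and 4 and 6 responders, the most extreme table has p = 2 × 6/28 = 0.43, so Fisher cannot reject there. Much of the gap at small n is therefore the discreteness of Fisher's test, which the SAP does not plan. The figures in step 2 do not have this fault.

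**The case against.** The strongest reply is that the analysis is exploratory and descriptive by design. The endpoint in 5.2.3 asks only for the relationship to be explored, and a table of "The number and proportion of GH responders" by status does that in part. Section 13.2.1 lists percent change by patient, 7.4 lists all data, and 3.3 allows further exploratory analyses. With so few subjects a reader could draw the plot from the listings, and a correlation would seldom be precise enough to change a conclusion. This stands as a limit on importance. It does not remove the mismatch: 5.1.3 says correlate, and choosing the analysis that answers an objective is the SAP's task.

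Two stronger readings are tempting and are not supported.

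- A reader might infer that cut-points will be chosen after responses are known, because the study is open-label and responder counts are reviewed repeatedly. Nothing in 15.2 says so. The status may be a category reported by the laboratory, or be defined in the protocol or a laboratory document that is not shown. What can be said is that 15.2 gives no definition and no reference to one.
- A reader might infer that a strong relation would be missed several times more often than with a rank correlation. That rests on a test the SAP does not plan, on unequal true error rates, and on an assumed high correlation.

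Two practical objections also stand and shape the remedy. Pooling 24 subjects would mix BID and TID, which the SAP presents as separate regimens. And if the assay reports only positive or negative, no correlation with an expression level can be computed.

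**Conclusion.** The concern holds as a mismatch between objective and analysis: 5.1.3 asks for a correlation of GH, IGF-1 and PRL responses with expression of three receptors, and 15.2 provides only responder counts by status. With a binary status about 29% to 41% of the information in a correlation is kept, so well over half is lost; with three ordered categories about half or somewhat more is lost. These figures assume roughly normal underlying variables, the responder rates in section 8 and receptor-positive shares of 25% to 75%. The SAP states neither the tissue count nor the number of categories nor an expected correlation. The point is minor: one exploratory objective is affected, and no primary or secondary result.

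**What to change.** In 15.2, for each of SSTR2, SSTR5 and D2, add:

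- a scatter plot of Day 14 percent change in GH (GHRGL), and likewise in IGF-1 and PRL, against the measured expression level or ordinal score, with points marked BID or TID;
- a Spearman rank correlation with 90% confidence interval, the level already used in 13.1 and 13.2, by regimen and, if both stages run, overall as a supplement;
- if the assay reports only positive or negative, the continuous percent changes by status in place of the correlation.

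Keep the category table, and cite the document that defines the expression categories or define them in the SAP.

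The cost is SAP wording and a small set of plots and tables, with no new visits, samples or subjects. The downsides are wide intervals and 3 receptors × 3 outcomes = 9 unadjusted correlations per regimen, so the results should be labelled exploratory and read as estimates rather than tests.

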### 5.2.2. Secondary Endpoints and Evaluations

- Assessment of safety and tolerability.
- Assessment of the proportion of subjects with GH  $< 1.0\mu\text{g/l}$  after 6-day titration plus 8-day treatment with BIM23B065 measured by mean serum concentration of GH over 6-hours at Day 14.
- Determination of the efficacy of BIM23B065 in reducing IGF-1 to  $< \text{ULN}$  (age normalised) after 6 day-titration and 8-day treatment period at Day 14 and Day 28.

*Statistical Analysis Plan*

*SD-BS-014, version 1.0*

*Parent document: SOP-BS-005*

*Page: 13 of 37*

**Protocol code:** D-FR-10380-002

**Protocol Title:** A phase IIA, open-label, single-arm, two stage, multi-centre study to investigate the pharmacodynamics, pharmacokinetics, safety and tolerability of repeated subcutaneous administration of BIM23B065 in subjects with acromegaly

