### 10.2. Definition of Baseline

Most baseline assessments will be performed on Day -1 (Visit 3) with some exceptions. In case the data of the planned baseline assessment is not available, the last assessment which precedes the first administration of the IMP will be used as a baseline.

*Statistical Analysis Plan*

*SD-BS-014, version 1.0*

*Parent document: SOP-BS-005*

**Protocol code:** D-FR-10380-002

**Protocol Title:** A phase IIA, open-label, single-arm, two stage, multi-centre study to investigate the pharmacodynamics, pharmacokinetics, safety and tolerability of repeated subcutaneous administration of BIM23B065 in subjects with acromegaly

- For the GH and PRL calculations the mean serum concentration will be used as baseline, collected over 6 hours on the Day -1. The baseline IGF-1 will be measured on Day -1.
- For antibodies anti-BIM23B065 the baseline will be the serum concentration taken prior to octreotide test dose, on V2.
- For other laboratory assessments (all endocrine and clinical laboratory assessments, parameters of glucose metabolism etc.) baseline will be the measurement of Day -1. At the parameters of glucose metabolism more baseline values will be used in accordance to the fasting condition or the relative time from meals (the fasting condition on Day -1 will be compared with the fasting condition of the studied day, while the assessment one hour after meal will be compared to the baseline (Day -1) one hour after meal measurement etc.).
- For BP and HR, orthostatic hypotonia, and ECG, the baseline will be the corresponding measurements on Day -1 at the same time points (i.e. time-matched). For Holter the baseline will be the assessment on Day -1.
- For gallbladder echography, the baseline will be the assessment during the screening period.
- For other results of the physical examination (body weight, body temperature etc.) the D-1 assessments will be the baseline.

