### **13.2.2. PD endpoints**

The IGF-1 and PRL measurements and the mean of the PRL concentration will be listed by patients and by visits along their change from baseline in percent.

Descriptive summaries will be presented for the measured concentration values and for the calculated percent change from baseline in the mITT set. Mean (+ SE) profiles over time will be displayed graphically.

The number and proportion (%) of subjects with IGF-1 < age normalized ULN, will be presented by visit along with the 90% Clopper-Pearson CI.

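### Section 15.2 judges PRL response by receptor status from the Day 14 value alone, ignoring Day -1; IGF-1 shares this only if normal baseline IGF-1 was allowed at entry

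*SAP*

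**What the plan says.** Section 5.1.3 sets the exploratory objective: "To correlate GH, Insulin-like Growth Factor-1 (IGF-1) and Prolactin (PRL) responses with expression of" SSTR2, SSTR5 and D2 in pituitary tumour tissue, where tissue exists. Section 5.2.3 gives the matching endpoint: "Exploration of the relationship between response to BIM23B065 and the expression of SSTR2, SSTR5 and D2 in those subjects with available tumour tissue". Both are framed as response to the drug.

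Section 15.2 is the only analysis of this objective that the SAP sets out. It tabulates three things by receptor expression status. The PRL measure reads: "subjects with a PRL<ULN (gender normalized) on Day 14 will be presented by the receptor expression status". The IGF-1 measure has the same form: "subjects with an IGF-1<ULN (age normalized) on Day 14". The third is the count of GH responders.

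Baselines for all three hormones are available. Section 10.2 fixes the PRL baseline as the 6-hour mean on Day -1, and adds: "The baseline IGF-1 will be measured on Day -1". Section 10.7 gives the percent-change formula. Section 13.2.2 applies it to IGF-1 and PRL: "Descriptive summaries will be presented for the measured concentration values and for the calculated percent change from baseline in the mITT set". That summary is not split by receptor status.

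**The concern.** A response is a change from where the subject started. PRL<ULN on Day 14 is a state, and it can be present before the first dose. Nothing in the SAP makes raised PRL a condition for entry or for inclusion in this table, and the SAP has no other PRL response criterion. The table therefore cannot separate subjects whom the drug normalised from subjects who were never abnormal. It also gives no credit for a large fall that ends just above the limit.

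What is at stake is how well this table answers its own question. If many subjects start with normal PRL, the proportions sit near their ceiling in every receptor category and a real relationship is hard to see. If the receptor groups differ in how many start normal, a difference can appear that has nothing to do with the drug. The tissue subset comes from at most 24 evaluable subjects (Section 8), so the choice of measure matters.

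**Working it through.** The SAP states no figure on this point, so there is none to reproduce. The power figure in Section 8 concerns the GH primary endpoint and has no bearing here.

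**Inputs.** From the SAP: the Day 14 criterion (15.2), the Day -1 baseline (10.2), and percent change = [1 - (present/baseline)] x 100 (10.7). Assumed, because the SAP gives no values: the share b of subjects with PRL<ULN on Day -1; that these subjects stay normal; and the normalisation rate q among subjects abnormal on Day -1.

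**One subject at a time** (invented values, in multiples of ULN):
- Subject A: 0.8 on Day -1 and 0.8 on Day 14. Percent change = [1 - 0.8/0.8] x 100 = 0%. Section 15.2 counts A as PRL<ULN.
- Subject B: 4.0 on Day -1 and 1.2 on Day 14. Percent change = [1 - 1.2/4.0] x 100 = 70%. Section 15.2 does not count B.

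The criterion ranks the unchanged subject above the one with the 70% fall.

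**A group.** Proportion with PRL<ULN on Day 14 = b + (1 - b) x q.

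With no drug effect (q = 0) this equals b. For two receptor groups with the same b, the tabulated difference is (1 - b) x (difference in q). Take q = 60% in receptor-positive and 0% in receptor-negative subjects:

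| b (assumed) | Receptor-positive | Receptor-negative | Tabulated difference | Abnormal on Day -1, per 12 subjects |
|---|---|---|---|---|
| 0% | 60% | 0% | 60 points | 12 |
| 25% | 70% | 25% | 45 points | 9 |
| 50% | 80% | 50% | 30 points | 6 |
| 75% | 90% | 75% | 15 points | 3 |
| 90% | 96% | 90% | 6 points | 1.2 |

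**Unequal baselines.** If q = 0 in both groups but b is 75% in one and 50% in the other, the table shows 75 - 50 = 25 points with no drug effect at all.

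**IGF-1.** The same formula applies, but b may be zero. Section 6.2 leaves eligibility to the protocol. If entry required IGF-1 at or above ULN, then b = 0 and the attenuation disappears. A fall that stops short of the limit is still not captured, as with subject B.

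**GH.** The GH responder definition in Section 13.1 already includes a reduction of at least 50% from baseline as one of its two branches, so this point does not extend to it.

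**The case against.** The strongest reply is that the table is exploratory and descriptive, in an opportunistic subset. No test or decision rule uses it: the interim rules in Section 7.2 rest on GH responders, safety and tolerability. That stands, and it sets the priority.

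A reader might also draw four stronger conclusions that the SAP does not support.

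- *That IGF-1 has the same flaw for certain.* Section 5.2.2 words the secondary endpoint as "Determination of the efficacy of BIM23B065 in reducing IGF-1 to" below the age-normalised limit, which suggests a raised starting value. The protocol may require one. Reusing that criterion in 15.2 is also consistent with the rest of the plan.
- *That the information is lost.* It is not. Section 13.2.2 lists IGF-1 and PRL by patient and visit with percent change, and Section 3.3 allows further exploratory analyses. The data can be matched to receptor status later. What is missing is a planned presentation; an unplanned one would be identified as such in the study report.
- *That the proportion mainly reflects baseline status.* This depends on b, which the SAP does not give. At b = 25%, 45 of the assumed 60 points remain.
- *That a specific D2-PRL question is defeated.* The SAP relates three hormones to three receptors without pairing D2 with PRL.

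**Conclusion.** The point holds for PRL as a mismatch of definition. The objective and endpoint concern response to the drug, and the only planned measure is a Day 14 status that takes no account of Day -1. This follows from the text and needs no assumed number.

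Its size cannot be fixed from the SAP. Under the assumption that baseline-normal subjects stay normal, the tabulated proportion is about b with no drug effect, and true differences in normalisation shrink by the factor 1 - b. For IGF-1 the attenuation is conditional on eligibility; only the failure to register partial falls is certain.

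This is a low-priority improvement to an exploratory table. It alters no primary or secondary conclusion.

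**What to change.** In Section 15.2:

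1. Add percent change from Day -1 to Day 14 in 6-hour mean PRL and in IGF-1, by SSTR2, SSTR5 and D2 status, as individual values and medians. Note in the table that under the Section 10.7 formula a fall is a positive number.
2. Keep the PRL<ULN and IGF-1<ULN counts on Day 14, but show baseline <ULN status alongside, so that subjects already normal are visible. Showing both is safer than dropping baseline-normal subjects, which could leave very few (3 of 12 at b = 75%, before any loss for missing tissue).
3. Leave the GH responder count as defined.

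The cost is SAP wording and one extra descriptive table. Baselines, samples and the percent-change derivation are already planned, and every subject with tissue and paired values contributes.
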